Methods: To accomplish Aim 1, we will expand the outline for the intervention into an initial treatment manual through meetings with content experts and stakeholder feedback. Next, we will develop fidelity checklists and revise the treatment manual through conducting the intervention with 2-3 couples. To accomplish Aims 2 and 3, we will evaluate the intervention in a non-randomized, open trial with 12 veterans diagnosed with PTSD and their loved ones. Veterans will complete baseline and posttreatment structured diagnostic interviews. Both members of the couple will complete baseline surveys, surveys during treatment, posttreatment surveys, and posttreatment qualitative exit interviews. Using data obtained from the open trial, we will assess the intervention's acceptability, feasibility, mechanisms, and outcomes. Upon completion of this proposal, we will be well positioned to apply for Merit funding for a randomized clinical trial (Stage 2 of the Stage Model of Treatment Development) of this innovative, exposure based, couple therapy.

List of Abbreviations, Acronyms, and Symbols

BFT	Behavioral Family Therapy
CAPS-5	Clinician-Administered PTSD Scale for DSM-5
CCDOR	Center for Care Delivery & Outcomes Research
CES	Credibility Expectancy Scale
CE	Studio Community Engagement Studio
Co-I	Co-Investigator
COACH	Teaching Loved Ones to Help Veterans Optimize their PTSD Care and Healing
CPT	Cognitive Processing Therapy
CSQ-8	Client Evaluation of Services Questionnaire
DSM-5	Diagnostic and Statistical Manual of Mental Disorders
DoD	Department of Defense
EBP	Evidence Based Psychotherapy
FES	Family Environment Scale
HSR&D	Health Services Research and Development
HW	Homework
IPF	Inventory of Psychological Functioning
IIR	Investigator-Initiated Research
IRB	Institutional Review Board
ICBT	Integrative Behavioral Couples Therapy
LO	Loved Ones
MI	Motivational Interviewing
MH	Mental Health
N/A	Not Applicable
OCD	Obsessive Compulsive Disorder
OEF	Operation Enduring Freedom
OIF	Operation Iraqi Freedom
OMHS	Office of Mental Health Services
PEAS	Patient Exposure and Response Prevention Adherence Scale
PCL	Posttraumatic Stress Disorder Checklist (DSM-IV)
PCL-5	Posttraumatic Stress Disorder Checklist (DSM-5)
PE	Prolonged Exposure
PHQ-9	Patient Health Questionnaire
PI	Principal Investigator
PTSD	Posttraumatic Stress Disorder
RCT	Randomized Controlled Trial
SCID-5-CT	Clinical Trials Version of the Structured Clinical Interview for DSM-5
VA	Veterans Affairs

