5.0 Study Procedures

5.1 Study Design

First, we will expand the treatment outline for COACH (see Appendix 1) into an initial treatment manual through meetings with content experts and stakeholder feedback. Next, we will develop fidelity checklists and revise the treatment manual through a "test run" with 2-3 couples. The resultant intervention will then be evaluated in an open trial with 12 veterans diagnosed with PTSD and their loved ones. During the course of the open trial, we will refine fidelity checklists and develop a provider training program. Using data obtained from the open trial, we will assess the intervention's acceptability, feasibility,⁴⁴ mechanisms, and outcomes. Lastly, using clinical observations, participant feedback from qualitative exit interviews, and additional stakeholder feedback, we will make final edits to the manual, yielding a manual suitable for a future RCT (Stage II Manual).²⁵ Upon completion of this proposal, we will be well positioned to apply for Merit funding for a randomized controlled efficacy trial.²⁵

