5.2E. Manual Refinement. For any psychosocial intervention, critical insight is gained through actual delivery of the treatment. we will conduct a “test run” of the treatment manual with 2-3 cases. Early experience with these test cases will help identify sections of the treatment manual that prove difficult to implement or are unclear. The PI ([name]) and study Co-Investigator ([name]) will serve as the study providers. Of note, while [name] is a licensed psychologist, she is a Research Service employee and does not currently have Minneapolis VA privileges. She will treat cases under this IRB protocol and under the supervision of a privileged VA provider. After completing each of the sessions, Drs. [name] and [name] will compose a memo for the larger team that identifies (1) what went well and why, (2) what proved more challenging and why, and (3) time stamps from session recordings that correspond to these observations. Memoranda will be sent out to the team of investigators in advance and discussed in weekly intervention refinement meetings. The team will brainstorm solutions to problems and identify expansions needed to the manual to capture clinical observations. This work will generate the key questions for veteran and LO stakeholder meetings. These meetings will focus on problems with implementing ideas within the manual (e.g., “How can we help couples do a given at-home exercise more effectively?”). The study PI will draft manual revisions and distribute revisions to the team to review. During this time, [name] will also draft initial fidelity checklists, which will be reviewed and refined in team meetings.

5.3 Open Trial.

5.3A. Sample Identification & Recruitment. Participants will be ten veterans with PTSD at the Minneapolis VA and their loved ones. Although the Stage Model of Treatment Development does not recommend a sample size for stage 1B activities, published accounts of psychotherapy treatment development frequently report on samples of ten to twelve participants.⁴⁸⁻⁵¹ Veterans must meet full criteria for PTSD on the CAPS-5⁵² and have been in an intimate relationship for the last six months. Both members of the couple must be willing to participate together in therapy and deny any episodes of severe relationship violence in the past year. We will exclude veterans who are typically excluded from trauma-focused treatment due to counter-indications, including severe substance use, uncontrolled psychosis or mania, and

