active suicidal or homicidal ideation, which should be the focus of clinical attention. Lastly, we will exclude dyads in which the loved one also screens positive for PTSD.

Clinic referrals, announcements to veteran groups, and strategically placed study fliers in appropriate clinic locations will provide our first-line recruitment source. We are proposing to enroll one couple per month over 10 months (months 9-18). Using similar inclusion/exclusion criteria and strategies in PE², our team has received 72 referrals over the past 10 months and randomized 18 dyads at the Minneapolis VA. Eleven of these cases have been in intimate relationships ($M = 1.10$ per month). Of note, we are proposing to start recruitment for COACH after PE² recruitment efforts are planned to end.

Veterans identified through the above-mentioned means will be sent a brochure describing the study and a cover letter, informing them they will be contacted and how to decline participation. They will then be contacted by telephone by a trained interviewer to discuss the study, for consent, and for initial screening including an assessment of the status of their intimate relationship. With permission, their loved one will be recruited and consented by telephone. Veterans remaining eligible (i.e., partner agrees to participate, denies intimate partner violence (IPV), and screens negative for PTSD) will be scheduled for a diagnostic interview (Clinician-Administered PTSD Scale for DSM-5, CAPS-5⁵²; Clinical Trials Version of the Structured Clinical Interview for DSM-5, SCID-5-CT).⁵³ Diagnostic interviews will be conducted by a study staff member with a master's degree in clinical or counseling psychology under the supervision of a licensed clinical psychologist from the study team. To ensure our sample is representative of those receiving PE, we will enroll at least three women and three OEF/OIF Veterans. To ease anticipated barriers to couples attending therapy sessions, we will offer compensation for costs for childcare and travel and offer participation through telemedicine.

5.4 Limitations and Design Considerations.

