Veterans will also complete a posttreatment structured clinical interview for PTSD symptoms.⁵² Veterans and LOs will also complete 90-minute semi-structured qualitative exit interviews. All interviews will be conducted in person or by phone, based on the interviewee's preference, and will be audio-recorded. Qualitative exit interviews (Appendix 2) will assess (1) attitudes about intervention components, structure (e.g., level of therapist contact), and materials (e.g., handouts), (2) acceptability and efficacy of COACH, including suggestions for intervention improvement, (3) engagement with COACH, including retention and barriers/facilitators to engaging with the program, (4) perceptions of the impact of the program on the intervention targets (e.g., functioning, social control, subjective norms, and LO reliance) and exploration of unexpected domains impacted by the program, and (5) the completeness and time burden of the survey battery. We will also extract the following administrative data: (1) the number of sessions attended (from electronic medical record; retention), (2) the number of participants screened each month (screening), and (3) the number of eligible Veterans and LOs who declined participation (recruitment), and therapists ratings of homework compliance using two

5.6A. Risk to Subjects

A.1. Human Subjects Involvement and Characteristics

We aim to enroll 12 Veterans with PTSD at the Minneapolis VA and their loved ones. Veterans must (1) meet full criteria for PTSD on the CAPS⁵² and (2) have been in an intimate relationship for the last six months. Both members of the couple must be (3) willing to participate together in therapy, and (4) deny any episodes of

items adapted from the Patient Exposure and Response Prevention Adherence Scale (PEAS) for Obsessive Compulsive Disorder (also a cognitive-behavioral exposure therapy).⁶²

Table A. Data Sources					
Reporter	Baseline	During Treatment	Posttreatment	3-month follow-up	
Veteran	Structured Interview	Surveys assessing symptoms, weekly questions in preparation for therapy sessions for therapists, and treatment mechanisms	Structured Interview	Online measures	
	Online survey measures		Online survey measures		
			Qualitative Interview		
LO	Online survey measures	Surveys assessing symptoms, weekly questions in preparation for therapy sessions for therapists, and treatment mechanisms	Online survey measures Qualitative Interview	Online measures	

A.3. Potential Risks

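### The open trial has ten couples in 5.3A but 12 in the abstract and 5.1, and the stated accrual plan matches only ten; secondarily, the 3-month survey is not carried into 6.1, Table 2 or 5.4

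*Combined protocol and SAP*

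**What the plan says.** **Sample size.** Under the open-trial heading, 5.3A states: "Participants will be ten veterans with PTSD at the Minneapolis VA and their loved ones". The Methods part of the abstract states: "we will evaluate the intervention in a non-randomized, open trial with 12 veterans diagnosed with PTSD and their loved ones". Section 5.1 agrees with the abstract: "The resultant intervention will then be evaluated in an open trial with 12 veterans diagnosed with PTSD and their loved ones". Section 5.6A (A.1) also gives 12, without naming the open trial: "We aim to enroll 12 Veterans with PTSD at the Minneapolis VA and their loved ones".

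**Test-run couples.** The abstract and 5.1 describe a test run with 2-3 couples, then the open trial. Section 5.2E places these couples under the same protocol; of one of the two study providers it says: "She will treat cases under this IRB protocol".

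**Accrual.** Section 5.3A plans: "We are proposing to enroll one couple per month over 10 months (months 9-18". In support it cites the team's ongoing PE² trial, which randomized 18 dyads in 10 months: "Eleven of these cases have been in intimate relationships", a mean of 1.10 per month. The open-trial enrollment row of Table 2 in 5.5 counts from 1 to 10.

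**3-month survey.** It is planned in 5.6A (A.2 and Table A), paid for in 5.6C and 5.8D, and given its own contact schedule in 6.4 (Table 4). The list of survey times in 6.1 ends with the survey due within four weeks of the last session. Table 2 in 5.5 has a row for posttreatment assessments and none for 3 months. Section 5.4 calls the design pre-post and says longer follow-up would cost sample size.

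**The concern.** A trial needs one planned size, and here the operative text gives two. Someone working from 5.3A and the timeline would plan for ten couples; someone working from the abstract or 5.1 would plan for 12. Nothing in the text says which prevails, and only one of the two has an accrual plan behind it. A later report would also have to say how many couples were planned, and could cite either number.

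The 3-month survey is a smaller matter of the same kind. The plan commits to it in several places, yet the data-collection section and the timeline do not show it, and the limitations section still defends its absence.

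**Working it through.** **1. Reproduce the plan's own figure.** Inputs from 5.3A: one couple per month, months 9 to 18.
- Months available: 18 − 9 + 1 = 10.
- Expected enrollment: 1 × 10 = 10.

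This equals the ten in 5.3A and the last number in the Table 2 enrollment row. In the text copy used here that row sits under months 4-13 rather than 9-18. Column alignment may have been lost in conversion, so only the count is used.

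**2. Try to reach 12 from the stated inputs.**
- Past rate: 11 / 10 = 1.10 per month; over 10 months, 1.10 × 10 = 11.
- Rate needed for 12 in 10 months: 12 / 10 = 1.2 per month.
- Time needed for 12 at 1.10 per month: 12 / 1.10 = 10.9 months.
- Time needed for 12 at 1.0 per month: 12 / 1.0 = 12 months, that is months 9 to 20 (9 + 12 − 1 = 20).

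Neither stated rate gives an expected 12 in the stated window.

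**3. Test whether the test-run couples explain the gap.** Ten plus two is 12 (ten plus three is 13). This could account for the figure in 5.6A, which does not name the open trial and may count everyone treated under the protocol. It cannot account for the abstract or 5.1, which put the 2-3 test couples first and then give 12 for the open trial itself. On that reading the protocol would treat 12 + 2 = 14 to 12 + 3 = 15 couples in all. Section 5.6A is therefore weaker evidence for 12 than the other two places.

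**4. Check whether the sample-size rationale settles it.** Section 5.3A refers to published samples of ten to twelve. That describes other studies. The protocol does not adopt a range; it states ten in one place and 12 in others. No alpha, power, effect size or dropout rate is given from which N could be recomputed.

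**5. Size of the gap.** 12 − 10 = 2 couples, which is 2 / 10 = 20% of ten, or 2 / 12 = 17% of 12.

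**6. The 3-month survey.**

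| Place | 3-month survey |
|---|---|
| 5.6A, A.2 and Table A | present |
| 5.6C and 5.8D, payments | present ($70) |
| 6.4, Table 4 | present, with contact schedule |
| 6.1 | absent |
| 5.5, Table 2 | absent |
| 5.4 | design called pre-post; longer follow-up argued against |

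The payment totals confirm that the survey is current. Veterans: 40 + 50 + 60 + 60 + 60 = 270, and 415 − 270 = 145. Loved ones: 40 + 60 + 60 = 160, and 305 − 160 = 145. The remainder is 70 + 3 × 25 = 145, assuming three monthly surveys. Without the $70 it would be 145 / 25 = 5.8 monthly surveys, which is not a whole number.

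**The case against.** The strongest reply is that little depends on the difference. Section 7.2 is descriptive throughout, with no test, threshold or go/no-go rule. Both numbers lie within the published range that 5.3A cites, and 5.6A speaks only of an aim. This stands, and it limits the consequence, but it does not make ten and 12 the same number.

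A second reply is that 12 could still be reached in the stated window. If accrual is assumed to be Poisson, the chance of 12 or more couples in 10 months is about 42% at 1.10 per month and about 30% at 1.0. This also stands: the rates show what to expect, not that 12 is out of reach. But a plan for 12 should have an accrual statement whose expectation is 12.

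A third reply is that the general recruitment row in Table 2 runs longer than the enrollment row, with about 17 marks. That row shows recruitment activity; the numbered enrollment row is the one that counts couples, and it stops at ten.

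On the survey, 6.4 already tells staff how to run it, and the pre-post label remains true of the structured interview, which Table A schedules only at baseline and posttreatment. Both points are fair and make this part secondary. The omission from 6.1 and Table 2, and the outdated argument in 5.4, remain.

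A reader might infer more than the documents support:
- **That ten enrolled would score as 100% of one target and 83% of the other.** Enrollment against target is not a listed measure. The recruitment and screening data are the number screened each month and the number of eligible people who declined.
- **That follow-up would overrun month 24.** No text ends data collection there, the lag from enrollment to first session is not stated, and the placement of the enrollment row in Table 2 is uncertain.
- **That the recruitment goals in 5.7C should be tied to the subgroup minimums in 5.3A ("we will enroll at least three women and three OEF/OIF Veterans").** No rule in the plan links them.

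**Conclusion.** The sample size is wrong as written in at least one place. Section 5.3A, its accrual plan and the Table 2 count agree on ten. The abstract and 5.1 say 12 for the same trial, with no accrual statement to match; 5.6A says 12 but may count differently. The gap is two couples. The cited past rate falls between the two figures, at an expected 11, and an expected 12 needs about 11 to 12 months, assuming a constant rate of 1.10 to 1.0 per month.

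The documents do not show which N is intended. Agreement with the accrual plan shows that ten is the figure the schedule was built on, not that 12 is the mistake. Nor do they support a claim of lost power: there is no hypothesis test and no power basis for either number.

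The 3-month survey is a real but secondary inconsistency: planned and paid for, but missing from two places and argued against in a third. The consequence of the whole point is modest, but a trial's planned size should not differ between sections, and restating it costs little.

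**What to change.** State one N for the open trial in the abstract, 5.1, 5.3A and 5.6A. In 5.6A, say whether test-run couples are counted; if they are, its total will exceed the open-trial N by two or three.

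- **If N is ten:** the accrual text in 5.3A and the Table 2 count stand. The cost is wording in the abstract, 5.1 and 5.6A.
- **If N is 12:** change 5.3A, and restate accrual there and in Table 2, either with a longer enrollment period (about 1 to 2 months more, in expectation) or with 1.2 couples per month and the basis for it. The cost is wording plus that extra time or justification.

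Secondarily, under either N, add the 3-month survey to the survey times in 6.1 and as a row in Table 2. Revise 5.4 so that it acknowledges the 3-month survey and no longer argues against longer follow-up as though none were planned. The cost is one table row and about one sentence in each section.

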5.6 Human Subjects

For all research activities involving human subjects, we will obtain approvals from the VA's Central Institutional Review Board (IRB) with local approvals from the Minneapolis VA as required through the Central IRB process.

Table 1. Abbreviated Measures (see Materials document for exhaustive list of measures and items)

Domain	Reporter		Source			Measure
	V	LO	S	I	A	
Acceptability						
Treatment Structure	X	X	X	X		CES ⁵⁶ ; CSQ-8 ⁵⁷
Materials	X	X		X		N/A
Feasibility						
Treatment Retention	X	X	X	X	N/A	

Treatment Fidelity		X	Fidelity instrument ^b
Screening Approach		X	N/A
Recruitment Approach		X	N/A
Assessment Process	X X	X X	All survey measures
Outcomes: Functioning			
Overall functioning	X X	X	Short Form Survey ⁵⁸
MH functioning	X X	X X	CAPS ⁵² , PCL-5 ⁵⁹ ; PHQ-9 ^{,60}
Self-care functioning	X X	X	IPF ⁵⁵
Family functioning	X X	X	IPF ⁵⁵
Romantic functioning	X X	X	IPF ⁵⁵
Communication	X X	X	Prepare/Enrich ⁶¹
Conflict Resolution	X X	X	Prepare/Enrich ⁶¹
Parenting	X X	X	IPF ⁵⁵
Social functioning	X X	X	IPF ⁵⁵
Outcomes: Mechanisms			
Session Attendance		X	N/A
HW Compliance		X	PEAS ⁶²
Social control	X X	X	Emotional and Problematic Support ⁶³
Subjective Norms	X X	X	Subjective Norms-PTSD ^a
LO Reliance	X X	X	Treatment Discussions ^a

^aUnpublished scale from Project HomeFront. ^bDeveloped during the study
 V = Veteran; LO = Loved One; A = Administrative data; S = Survey; I = Interview.

severe relationship violence in the past year. We will exclude veterans who are typically excluded from trauma-focused treatment due to counter-indications, including (1) severe substance use, (2) uncontrolled psychosis or mania, and (3) active suicidal or homicidal ideation, which should be the focus of clinical attention. Lastly, (4) we will exclude dyads in which the loved one also screens positive for PTSD. See below for exhaustive list of inclusions/exclusions.

A.2. Data Sources

Data sources will include surveys, semi-structured qualitative interviews, and administrative data. Veterans and their LOs will complete surveys prior to treatment (baseline), during treatment, after their final COACH session, and 3-months after their final COACH session. Those who do not attend their final session will receive their survey by mail or email (Qualtrics link) using CCDOR's modified-Dillman protocol.⁵⁴

Veterans will also complete a posttreatment structured clinical interview for PTSD symptoms.⁵² Veterans and LOs will also complete 90-minute semi-structured qualitative exit interviews. All interviews will be conducted in person or by phone, based on the interviewee's preference, and will be audio-recorded. Qualitative exit interviews (Appendix 2) will assess (1) attitudes about intervention components, structure (e.g., level of therapist contact), and materials (e.g., handouts), (2) acceptability and efficacy of COACH, including suggestions for intervention improvement, (3) engagement with COACH, including retention and barriers/facilitators to engaging with the program, (4) perceptions of the impact of the program on the intervention targets (e.g., functioning, social control, subjective norms, and LO reliance) and exploration of unexpected domains impacted by the program, and (5) the completeness and time burden of the survey battery. We will also extract the following administrative data: (1) the number of sessions attended (from electronic medical record; retention), (2) the number of participants screened each month (screening), and (3) the number of eligible Veterans and LOs who declined participation (recruitment), and therapists ratings of homework compliance using two

5.6A. Risk to Subjects

A.1. Human Subjects Involvement and Characteristics

We aim to enroll 12 Veterans with PTSD at the Minneapolis VA and their loved ones. Veterans must (1) meet full criteria for PTSD on the CAPS⁵² and (2) have been in an intimate relationship for the last six months. Both members of the couple must be (3) willing to participate together in therapy, and (4) deny any episodes of

items adapted from the Patient Exposure and Response Prevention Adherence Scale (PEAS) for Obsessive Compulsive Disorder (also a cognitive-behavioral exposure therapy).⁶²

Table A. Data Sources					
Reporter	Baseline	During Treatment	Posttreatment	3-month follow-up	
Veteran	Structured Interview	Surveys assessing symptoms, weekly questions in preparation for therapy sessions for therapists, and treatment mechanisms	Structured Interview	Online measures	
	Online survey measures		Online survey measures		
			Qualitative Interview		
LO	Online survey measures	Surveys assessing symptoms, weekly questions in preparation for therapy sessions for therapists, and treatment mechanisms	Online survey measures Qualitative Interview	Online measures	

A.3. Potential Risks

This study involves minimal risk. COACH is a flexible length cognitive-behavioral, loved one-assisted, treatment for PTSD that draws from PE, ICBT, and PE². Treatment is typically between 13 and 15 sessions, but can be fewer or more based on patient need and symptom response. There are no anticipated physical risks in this study. Economic risks include potential loss of wages when traveling to and participating in the research intervention. The questionnaires ask questions consistent with those included in routine clinical care, and participants can refuse to answer any question(s). Individuals may experience some psychological or social discomfort during the course of the study; however, the intervention is likely to increase their well-being. Additionally, the risks are no greater than those encountered in routine clinical care.

5.6B. Protection Against Risk

B.1. Social and Psychological

Appropriate safeguards will be in place if screening interviews, assessments, interviews, or therapy sessions cause any psychological distress, a psychiatric emergency emerges among participants, or severe interpersonal violence (SIV) is reported. Severe violence will be defined as one or more episodes of severe violence in the past year (e.g., beating up, threatening with a knife or gun). The PI has expertise in assessing and managing risk for SIV, including within a clinical trial, and will closely train and supervise study staff in assessing and managing risk for SIV.

All surveys will be screened upon receipt by study staff. If a psychiatric emergency is reported on surveys (i.e., expression of risk for suicide or homicide), veterans MH providers will be notified. MH providers will follow-up as they deem clinically indicated. If the participant does not

have a MH provider or this provider cannot be reached, the site PI, or in case of her unavailability, a Co-I will contact the disclosing participant by phone, assess for risk and safety, and provide the participant with appropriate referrals. We will utilize access to local and national mental health resources available through the VA, including the suicide prevention hotline, risk assessments through Mental Health during regular business hours (Psychiatry Urgent Care), or the facility's Emergency Room during off hours. In the unusual event of an on-site psychiatric emergency involving a participant who is not a Veteran, including threats of or acute risk for SIV, the participant will be triaged within VA facilities. If indicated based on psychiatric evaluation, non-Veterans will be transferred for appropriate care in community. Once stabilized, they will be eligible to enter or re-enter the study.

All staff with contact with study participants will be trained on how to recognize, assess, and intervene, in a manner appropriate to their training backgrounds, in the case of a psychiatric emergency. They will be trained and supervised by an on-site licensed clinical psychologist and study team member (Co-I or PI).

If IPV is directly reported to a study staff member (e.g., during a screening call), the study staff member will (1) ensure the participant is speaking privately (e.g., if disclosed by phone), (2) ask if the participant currently feels safe, (3) offer immediate assistance (i.e., warm transfer to the national domestic violence hotline or contact the police), (4) offer to have a MH provider from the study reach out, and (5) offer local and national resources for IPV.

MH providers on the study will receive training on how to assess and intervene when IPV is reported. This includes training on assessing IPV severity and intervening on IPV, including safety plans, no aggression contracts, and time out procedures. When IPV is reported to a study MH Provider, they will discuss it privately with the reporter and intervene as clinically indicated, keeping the safety of the reporter of paramount concern. Providers will not breech the reporter's confidentiality unless they have the reporter's verbal permission or are concerned they must do so to prevent imminent harm.

All potential collaborators and study therapists on these research activities will have completed comprehensive training in the areas of research ethics, protection of human subjects, and suicide prevention. They will also have completed all VA required trainings pertinent to cyber security, VHA privacy policy (HIPAA), research data security and privacy, ethical principles of human subjects' protection, good clinical practice, and suicide prevention. In addition, [name] graduate coursework included a three-credit course on ethics.

IPV reports on surveys. Surveys ask about intimate partner violence (IPV). IPV reports are not routinely considered psychiatric emergencies that warrant breaching participants' confidentiality. Additionally, reaching out to all those who endorse IPV may have unintended negative consequences. Reaching out when uninvited to ask IPV victims to further discuss their IPV may be distressing and bring up traumatic memories. The outreach may be unwelcome, perceived as intrusive, and discourage future reporting. Discussing violence over the phone may also place the victim at risk to be overheard by the abuser, other loved ones, or children in the home. Consequently, a list of resources will be provided to participants, including for IPV.

Correspondence accompanying surveys will encourage respondents to contact study staff if they would like to discuss any of their survey responses. We will rely on participants to contact study staff if they wish to discuss their IPV experiences further. If participants are excluded due

to IPV, the staff member notifying the reporter of their exclusion will offer local and national resources for IPV.

Managing risk from CBOCs and in-home video telehealth sessions. Due to the nature and distance between the Veteran and telemental health provider incurred in telemedicine practice, additional measures will be taken to ensure patient safety. These procedures will be in place during all telemedicine sessions:

- a. Study providers will follow the guidelines detailed in the 2017 Department of Veteran Affairs National Telemental Health Supplement and the 2012 Telemental Health Suicide Prevention and Emergency Care manual.
- b. All study providers will follow the Minneapolis VA's local telemental health policies and emergency procedures at each facility and clinic.
- c. Telemental health provider will have detailed contact information from the patient with particular attention to who could be contacted in the event of an emergency. All emergency contact information, local police phone numbers and local emergency room contact information should be readily retrievable during all sessions.
- d. Providers will use the National Telehealth Help Desk when necessary: [name].

Additional manners to manage risk from CBOCs.

- a. For all telemental health sessions at CBOC locations, a CBOC staff person will be available to assist Veteran should the need arise.
- b. CBOC staff will be available by telephone for the remote telemedicine study provider should they need to emergently contact an on-site VA staff.
- c. If a patient becomes suicidal, homicidal, psychotic, or agitated, the Telehealth provider will ask for assistance from the CBOC staff who would help in deescalating the patient and/or initiating commitment.

Additionally, the study will abide by the requirements contained in the VHA Handbook for the credentialing of VHA practitioners who provide clinical services using telemedicine. All practitioners treating patients using telemedicine will be qualified to deliver the level of consultation, care, and treatment involved.

B.2. Economic:

Participants may choose to take time off work or may incur transportation costs because of participating in this study. Every effort will be taken to schedule assessments and therapy sessions at times convenient to participants to minimize loss of wages.

B.3. Loss of Confidentiality

DATA SECURITY. All data will be stored on the servers of the Center for Chronic Diseases Outcomes Research (CCDOR) at the Minneapolis VAHCS. CCDOR has well-established procedures to protect the privacy of research participants. Names, social security numbers, and contact information will not appear on any study materials. Instead, only unique study identification numbers randomly assigned to each unique record will be used. Only lead investigators, project coordinators, and study programmers (when extracting data to obtain treatment adherence and compare survey responders to non-responders for the survey) will have access to an encrypted crosswalk table linking study identification numbers to identifying information. The CCDOR Statistical and Data Management (SDM) team, in partnership with IRM staff, maintain several secure servers, access to which is granted only to SDM members who have been screened and assigned appropriate security clearance to work with patient data.

One common-access server contains individual project data. Access to individual project data on this server is granted only to project staff by an SDM team member, as authorized by the study investigator. Identifiers will be destroyed as quickly as possible. Audio and video recordings will be stored digitally on CCDOR servers and only accessible to the principal investigator and project coordinator. Participants will be asked not to use last names or provide identifying information during recorded interviews.

CONFIDENTIALITY. For all projects, strict confidentiality procedures will be maintained to minimize the potential risk of loss of confidentiality. Participant privacy will be further assured by conducting interviews in a private office and by assigning arbitrary identifiers in place of individual names in the field notes. Data analysis, interpretation, and reporting will be based on these de-identified field notes and transcriptions. Since subject responses will not be linked to identifying information, participant confidentiality will be assured. The time commitment will be explained to all participants prior to their participation in the study. Every effort will be made to minimize the length of time and maximize the convenience of the interviews. Participants will be assured that participation is completely voluntary and that they have the right to stop participation, decline answering any questions, or change the course of the interviews for any reason, including potential feelings of discomfort.

5.6C. Potential Benefits of the Proposed Research to the Subject and Others

Participants will receive \$40 for participating in Baseline surveys, \$50 for baseline diagnostic interviews (Veterans only), \$60 for posttreatment surveys, \$60 for posttreatment diagnostic interviews (Veterans only), and \$60 for one-time qualitative exit interviews. Both veterans and intimate partners will complete monthly surveys for outcomes and treatment mechanisms. They will receive \$25 for each of these surveys. Additionally, participants receive \$70 for completing a 3-month follow-up survey. A possible total of \$415 for veterans and \$305 for loved ones.

5.6D. Importance of Knowledge to be Gained

The influence of a successful course of PTSD treatment on a Veteran's life is considerable. In addition to reducing symptoms of PTSD and associated mental health problems (e.g., depression), successful PTSD treatment improves reduces, and may even reverse, the negative physical health effects associated with PTSD.^{10,41} Family involvement has been highlighted as a fertile avenue for improving the outcomes for patients with PTSD.^{7,27} Yet, despite congressional legislation and national mandates within VA/DoD for family involvement in PTSD care,^{7,8,42,43} family inclusion in PE and CPT is infrequent (17% among HomeFront veterans). Concordant with the Behavioral Health & Social Reintegration Program, this proposal will support work an intervention intended to promote higher rates of recovery from PTSD, better overall functioning, greater family functioning, and greater social functioning. These outcomes are consistent with those patients likely find meaningful.²⁷ Our stakeholder engagement strategies, described below, provide an additional pathway to ensuring COACH aligns with what LOs, providers, and VA leadership need in a family intervention for PTSD, building a more patient-centered approach to treating PTSD. Overall, this work is highly is consistent with the explicit goals of the Behavioral Health & Social Reintegration Program to promote research that uses "family support as a means to reintegration" and leads veterans to "function more fully in society" and "embrace social situations".

5.6E. Data and Safety Monitoring Plan

This project will operate under the oversight of the Minneapolis VA Health Care System's IRB for Protection of Human Subjects. The IRB reviews research projects which involve human subjects to ensure that two broad standards are upheld: first, that subjects are not placed at undue risk; second, that they give uncoerced, informed consent to their participation. After initial review, each approved project is re-evaluated annually. The Minneapolis VA Health Care System's IRB works with investigators to modify projects to ensure adequate protection for its subjects' welfare and right of self-determination. VA regulations require that all investigators and individuals who work on the study undergo comprehensive training annually in research integrity and protection of human subjects.

E.1. Privacy Protections:

CCDOR protects data collected for the purpose of conducting research projects at a level higher than that provided for clinical encounters. We use "stand-alone," secure data servers that are accessible only to designated, security-cleared, and trained personnel and data are de-identified as quickly as is feasible. Details about CCDOR's specific data privacy assurance procedures to be employed for this study are provided below.

E.2. Maintaining Secure Servers:

CCDOR maintains three secure computer servers that are protected under the Minneapolis VA Windows 2000 network. All individuals with administrative access privileges to CCDOR's servers, including IRM personnel and the CCDOR Statistical & Data Management Team, have been screened and assigned a security clearance putting them in trusted positions of the hospital with clearances to work with patient level data. These individuals and their access to the CCDOR servers is ultimately monitored and controlled by [name], Senior Program Analyst for the CCDOR Statistical & Data Management Team. IRM's access to the data is strictly limited to backing up server data, which prevents catastrophic loss of data. Backups are written to tapes that are stored in a secure location accessible only to IRM personnel. CCDOR's Statistical & Data Management Team members maintain permissions, data storage, and all server applications.

